1.4. Benefit-Risk Assessment

Benefits

The clinical effect of efgartigimod was explored using clinical activity tools commonly used in MG clinical research and practice: total MG-ADL, QMG, MGC, and MG-QoL15r scores. A mean total score change from baseline in total MG-ADL, QMG, MGC, and MG-QoL15r scores was observed as early as day 8 in patients treated with efgartigimod. A long-lasting reduction in total MG-ADL and MGC scores was observed, with the reduction in total scores still seen at day 78 (end of study [EoS]). Efgartigimod showed a statistically significant reduction in total MG-ADL, QMG, and MG-QoL15r scores compared with placebo at specific time points, indicating a clinical improvement in efgartigimod treatment over placebo. For all MG scales, a greater maximum mean change from baseline (reduction) was observed in the efgartigimod treatment group compared with placebo.

Eligible participants of trial ARGX-113-1704 will be offered the option to roll over to this follow-on trial where (re-)treatment of efgartigimod can be done on an “as needed basis,” which is a substantial benefit for the patient.

Patients who have completed at least 1 cycle of treatment and at least 1 year of trial ARGX-113-1705 and have started Part B are eligible to enroll in the open-label trial ARGX-113-2002 to receive efgartigimod by SC administration. SC administration is considered more convenient for patients than IV administration, especially if efgartigimod can be administered by the patient or caregiver at home.

Risks

No major safety findings have arisen in the ongoing and completed trials, nor any pattern of AEs which would raise concerns or alter the potential benefit-risk profile of efgartigimod.

In the phase 3 trials in patients with gMG, the majority of TEAEs were reported as mild (grade 1) or moderate (grade 2) in severity. The most frequently ($\geq 5\%$) reported TEAEs during all cycles of efgartigimod 10 mg/kg treatment in the overall population who received at least 1 dose of efgartigimod were headache, nasopharyngitis, upper respiratory tract infection, diarrhea, urinary tract infection, nausea, myalgia, and oropharyngeal pain. TEAEs of severity of grade ≥ 3 that occurred in >2 patients who received efgartigimod were headache and myasthenia gravis. The only TEAE that led to efgartigimod discontinuation reported in >2 patients was myasthenia gravis. No SAEs were assessed by the investigator as related to efgartigimod treatment.

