3. TRIAL ENDPOINTS

3.1. Primary Endpoint

Incidence and severity of AEs, serious adverse events (SAEs), vital signs, ECG and laboratory assessments over the duration of the trial in AChR-Ab seropositive patients.

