5.1. Informed Consent and Roll-Over Visit

The roll-over visit (SEB) can be either ITP₀V₁ or TP₁V₁, depending on the patient status regarding the need for (re-)treatment upon roll-over from trial ARGX-113-1704. The first visit in trial ARGX-113-1705 will always coincide with the last visit in trial ARGX-113-1704.

The patient must sign the informed consent form (ICF) prior to any trial-related assessment. The assessments done for the last visit in trial ARGX-113-1704 should not be repeated.

Prior to signing the ICF, trial patients will be instructed not to participate in any other clinical trial that involves an intervention or collection of data until the completion of the current trial.

After informed consent has been obtained, participants of trial ARGX-113-1704 will be screened at the site for eligibility to roll over to this trial based on the inclusion and exclusion criteria defined in Sections 4.3.1 and 4.3.2, respectively.

In addition to obtaining written informed consent and the eligibility check, the following assessments will be performed at SEB:

- Clinically relevant medical and surgical history, clinically relevant prior treatments and all concomitant medications (see Sections 6.8 and 7.2.5)
- Demographic characteristics (date of birth, sex, race, and ethnicity, per national regulations)
- Assessments of disease severity – the MG-ADL scale should be administered before the QMG scale
- Suicidal ideation and behavior will be assessed via a targeted question based on the Patient Health Questionnaire item 9 (PHQ-9)¹⁷
- Complete physical examination, including at a minimum: general appearance, skin, lymph nodes, musculoskeletal/extremities, abdomen, cardiovascular, respiratory, and neurological systems
- Weight and height
- Vital signs (supine blood pressure, heart rate, body temperature). It is recommended that the method used to measure body temperature at SEB is maintained throughout the trial for each patient
- ECG (heart rate, PR, QT, and QRS interval)
- Clinical laboratory tests (see Appendix 3 for an overview of the clinical laboratory tests that will be assessed). Patients need to have fasted at least 8 hours prior to sampling
- Urinalysis
- Urine pregnancy test (only for women of childbearing potential, see DEFINITION OF TERMS)

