7.2.1. Adverse Events

The investigator is responsible for recording all AEs observed during the trial from the time the patient signs the ICF until the last contact of the patient.

Definition of AE: An AE is any untoward medical occurrence in a clinical trial patient whether or not a pharmaceutical product is administered, and which does not necessarily have a causal relationship with this treatment. An AE can therefore be any unfavorable and unintended sign (including an abnormal laboratory finding), symptom, or disease temporally associated with the use of a medicinal product or efgartigimod, whether or not considered related to the medicinal product or efgartigimod.

An AE can also be a new disease or exacerbation of an existing disease (a worsening in the character, frequency, or severity of a known condition), if considered clinically relevant by the investigator.

Abnormal laboratory values, or test results, physical examination findings, and other abnormal investigational findings (ie, ECG) should not be reported as AEs unless they are considered clinically significant, eg, require therapy (eg, hematologic abnormality that requires transfusion or hematological stem cell support) or lead to treatment discontinuation.

Death is not considered an AE but an outcome.

MG disease worsening, if considered clinically relevant by the investigator, can be reported as AE, provided that it is supported by a clinically relevant change in total MG-ADL score (as compared to SEB). The investigator should contact the sponsor in case of clinically relevant worsening of the disease.

Adverse Drug Reaction (ADR): Any untoward and unintended response in a patient to efgartigimod, which is related to any dose administered to that patient.

Definition of Serious AE (SAE): An SAE, experience or reaction, is any untoward medical occurrence (whether considered to be related to efgartigimod or not) that at any dose:

- Results in death
- Is life-threatening (the patient is at a risk of death at the time of the event; it does not refer to an event, which hypothetically might have caused death if it was more severe)
- Requires inpatient hospitalization or prolongation of existing hospitalization. However, a planned hospitalization related to the administration of efgartigimod is not considered an SAE

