(Hospital admissions and/or surgical operations planned before a trial are not considered SAEs or if the illness or disease, which caused hospitalization, existed before the patient was enrolled in the trial, provided that it did not deteriorate in an unexpected way during the trial. However, the condition for which the surgery is required may be an AE.)

- Results in persistent or significant disability or incapacity, OR
- Is a congenital abnormality or birth defect

- Other: Medically significant events, which do not meet any of the criteria above, but may jeopardize the patient and may require medical or surgical intervention to prevent 1 of the other serious outcomes listed in the definition above. Examples of such events are blood dyscrasias (eg, neutropenia or anemia requiring blood transfusion, etc.) or convulsions that do not result in inpatient hospitalization

Suspected Unexpected Serious Adverse Reactions (SUSARs) and Unexpected Adverse Reactions: Any suspected adverse reaction that is serious, unexpected, and considered to be related to drug exposure is defined as a SUSAR.

An unexpected AE is any adverse drug event, which is not listed in the current IB or is not listed at the specificity or intensity that has been observed.

Suspected adverse reaction means any AE for which there is a reasonable possibility that the drug caused the AE.

An untoward and unintended post-dosing response to a non-trial drug is, by definition, not a SUSAR, but is, however, an AE.

Each AE is to be evaluated for duration, severity, seriousness and causal relationship to efgartigimod or trial procedures. The action taken with the investigational drug and the outcome of the event must also be recorded.

Treatment-emergent adverse event (TEAE): Any AE temporally associated with the use of efgartigimod, whether considered related to efgartigimod or not. TEAEs are recorded from the start of efgartigimod administration, until completion of the patient's last visit.

Overdose

For the purposes of this trial, exceeding the dosage requirements specified in this protocol (see Section 6.1) represents an overdose. In case of suspected overdose, the patient should be treated according to standard medical practice based on the investigator's judgment.

Severity

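### The hospitalisation exemption in the SAE definition can be read to cover unplanned admissions for a pre-existing illness, gMG included, so such admissions can be flagged non-serious, and differently across sites

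*Protocol*

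**What the plan says.** Protocol 7.2.1 (definition of a serious AE) lists hospitalisation among the seriousness criteria: "Requires inpatient hospitalization or prolongation of existing hospitalization". The same bullet excludes a planned stay for giving efgartigimod. A parenthesis then widens the exclusion. It speaks of admissions and operations "planned before a trial are not considered SAEs or if the illness or disease, which caused hospitalization", and continues, of that illness, that it "existed before the patient was enrolled in the trial, provided that it did not deteriorate in an unexpected way during the trial". It closes by allowing that a condition needing surgery may itself be an AE.

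The nearest definition of unexpectedness, later in 7.2.1, serves SUSAR classification: "An unexpected AE is any adverse drug event, which is not listed in the current IB". It concerns drug events compared with the Investigator's Brochure, not the course of a pre-existing disease.

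The primary endpoint (Protocol 3.1) is "Incidence and severity of AEs, serious adverse events (SAEs), vital signs, ECG and laboratory assessments over the duration of the trial", in AChR-Ab seropositive patients. The secondary endpoint (3.2) is the same in the overall population. SAP 5.1.1 takes seriousness from a recorded flag, and SAP 5.1.2 allocates each AE to the period in which it started. SAP 8.1 lists tables of serious (14.3.1.3), non-serious (14.3.1.4) and Grade 3 or higher TEAEs (14.3.1.5), but none of hospitalisations.

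**The concern.** Seriousness is meant to be a matter of outcome: was the patient admitted? The parenthesis adds a second question, whether the underlying illness worsened unexpectedly, and leaves it undefined. In a trial where every patient has the same relapsing disease, that question decides how the most foreseeable kind of admission is classified.

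SAE incidence is part of the primary endpoint, and there is no control arm in which the same classification rule would apply. If one site flags an MG admission as serious and another does not, the reported percentage depends partly on how each read one sentence. The 24-hour reporting duty in Protocol 7.2.1.2 attaches to SAEs, so it depends on the same reading.

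MG worsening is a material event in this programme. Protocol 1.4 says that "The only TEAE that led to efgartigimod discontinuation reported in >2 patients was myasthenia gravis". It also names MG among the Grade 3 or higher TEAEs seen in more than 2 patients.

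**Working it through.** There is no plan figure to reproduce: Protocol 8.1 gives sample size as not applicable, and the analysis is descriptive. The check is of wording.

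1. **Reach of the second alternative.** The two halves of the parenthesis are joined by *or*, and *planned* appears only in the first. If *planned* governed both, the second half would add little, because the first already exempts every admission planned beforehand. Read literally, the second half covers unplanned admissions. The sentence is ungrammatical, however, so the reading is open rather than settled.

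2. **The test for leaving the exemption.** The only way out is unexpected deterioration, which is not defined for a pre-existing disease. The protocol itself anticipates MG worsening: re-treatment in Part A starts when symptoms return (4.1), clinical deterioration is defined for rescue (6.8.2), and exacerbation and crisis are described as part of the disease (1.3). An investigator could reasonably call ordinary worsening expected.

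3. **Who has a pre-existing illness.** All participants have gMG. In addition, "The first visit in trial ARGX-113-1705 will always coincide with the last visit in trial ARGX-113-1704" (5.1), and conditions present before study entry baseline go to medical history (7.2.5). A condition that began during ARGX-113-1704 therefore also predates enrolment here.

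4. **What still counts as serious.** The parenthesis qualifies the hospitalisation bullet only. Death, disability and medically significant events are separate criteria, as is the one reading "Is life-threatening (the patient is at a risk of death at the time of the event". The exposed group is admissions for which hospitalisation is the sole reason for seriousness.

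5. **What the analysis does with them.** An exempted admission recorded as an AE carries a non-serious flag. It leaves 14.3.1.3, enters 14.3.1.4, and may enter 14.3.1.5, since the general Grade 3 description in 7.2.1 includes hospitalisation. MG worsening only *can* be reported as an AE, if judged clinically relevant and supported by an MG-ADL change from study entry baseline, so recording is not assured. For a condition carried over from ARGX-113-1704, allocation by start date (SAP 5.1.2) means it reaches the serious TEAE table only if its worsening is recorded as a new AE. Events in the period before the first cycle are only listed (SAP 5.1.3).

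6. **Size.** The documents give no number of admissions, for MG or otherwise. Only a scale can be stated: each patient whose sole SAE is an exempted admission lowers overall SAE incidence by 1/N. SAP 1.3 puts N at no more than 167 in the overall population, and the seropositive safety set can be no larger. The step is therefore at least 1/167 = 0.6 percentage points per such patient. How many such patients there are is unknown.

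**The case against.** The opening about planned admissions and the closing words about surgery suggest that the authors had elective procedures in mind, and many sites may read it that way. This is fair. It makes the point one of ambiguity, and ambiguity is what lets sites diverge.

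A reader might infer that MG crises vanish from the SAE count. The text does not support that: a crisis that puts life at risk is serious under a separate criterion. The medically significant criterion also covers events that may jeopardise the patient, and Part A rescue requires the physician to believe that health is in jeopardy (6.8.2). Many unplanned MG admissions should therefore be serious by another route, although that criterion is itself a judgement.

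A reader might also infer that each investigator decides unaided. Protocol 7.2.1 asks the investigator to contact the sponsor about clinically relevant worsening. Section 7.2.1.4 lets the sponsor's designee follow up non-serious AEs, for example through discharge summaries, and the DSMB reviews all safety data (7.2.6). These safeguards reduce the risk but do not tell anyone how to apply the exemption.

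The table of serious treatment-related TEAEs (14.3.1.8) is unlikely to change much. An admission put down to disease progression fits the protocol's *unlikely* category, which is reported as unrelated.

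**Conclusion.** The concern holds as a wording defect with a possible effect on the primary and secondary endpoints. Applied as written, 7.2.1 allows an unplanned admission for a pre-existing illness to be flagged non-serious when hospitalisation is the only seriousness criterion met, and it allows sites to differ. The SAP has no step that would restore such events to the serious tables.

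The conclusion rests on the literal reading of the parenthesis and on some investigators treating MG worsening as expected. It is tempting to go further and say that SAE incidence is under-counted, or to attach a percentage. The documents support neither. Protocol 1.4 reports severity, discontinuations and deaths, not admissions or how they were flagged. It also shows that MG events are being reported as AEs. The loss, if any, is from the SAE component; exempted events that are recorded still contribute to AE incidence and severity. The carry-over from ARGX-113-1704 is a secondary part of the point, because recording and start-date rules already limit what reaches the table.

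**What to change.** In Protocol 7.2.1:

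- Limit the exemption to admissions or operations planned before ICF signature for a condition that has not worsened since.
- Delete the unexpectedness proviso.
- State that an unplanned admission or prolongation for worsening of a pre-existing condition, including MG or an AE ongoing from ARGX-113-1704, is recorded as a new AE with its own start date and flagged serious. The new start date matters: without it, SAP 5.1.2 would not place a carried-over condition in the serious TEAE table.

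Before database lock, query AEs recorded as non-serious that involved an inpatient stay and correct the flag. The AE items named in Protocol 7.2.1.2 do not include an admission field, so sites may have to be asked. Non-serious Grade 3 or higher events and MG terms are a sensible place to start. The query cannot recover an admission never recorded as an AE.

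The cost is a short change to one section, a site notice and a small data query. The reported SAE percentage may be somewhat higher.

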Exacerbations of MG are treated using either therapeutic plasma exchange (PLEX), immunoadsorption or IVIg. In the case of PLEX, typically 1 exchange, removing 1 to 2 plasma volumes, is done every other day up to a total of 4 to 6 times, to improve muscle strength or ameliorate a myasthenic crisis. Unfortunately, this treatment is invasive and has frequent side effects such as hypotension, paresthesia, infections, and thrombotic complications. IVIg is widely used for patients with exacerbating MG. The mechanism of action of IVIg in MG is still unclear and may include interference with autoantibodies, B-cell modulation, saturation of FcRn and complement.^{13,14} In addition, the use of IVIg is burdensome for the patient.

These approaches however are not always available in all clinical centers since they require specific facilities and instrumentation.^{2,3}

Finally, in selected cases, surgical removal of the thymus gland is also used to ameliorate the clinical manifestations of MG. However, thymectomy is not always effective in all patients and is associated with surgery-specific risks.^{2,3,15,16}

Following administration of efgartigimod (10 mg/kg) in 4 infusions administered 1 week apart in addition to SoC in patients with autoimmune MG with generalized muscle weakness in the phase 2 trial (ARGX-113-1602, also see Section 1.2), overall efgartigimod was well tolerated and demonstrated a good safety profile consistent with phase 1 data. No serious or severe AEs were reported. The following events were reported as related to efgartigimod administration: rhinorrhea, gingivitis, headache, nausea, pruritus, paresthesia, myalgia, lymphocyte count decreased, monocyte count decreased, neutrophil count decreased, contusion, feeling hot, infusion site pain and pruritus, and herpes zoster. All these events were reported as mild, except the herpes zoster, which was considered as moderate and occurred in a patient concomitantly treated with a systemic corticosteroid and NSID. Efgartigimod demonstrated a relevant and long-lasting improvement over placebo of the clinical manifestations of MG as measured by all 4 clinical efficacy MG scales, which reached statistical significance at specific timepoints on the MG-ADL, QMG, and MGQoL15r scales. Pharmacokinetic, PD, and immunogenicity profiles were consistent with phase 1 data. In addition, a potent and long-lasting reduction of AChR autoantibodies was observed.

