All AEs observed will be graded using the National Cancer Institute (NCI) Common Terminology Criteria for Adverse Events (CTCAE) version 5.0. The NCI-CTCAE is a descriptive terminology, which can be utilized for AE reporting. A grading (severity) scale is provided for each AE term. Grade refers to the severity of the AE. If a particular AE's severity is not specifically graded by the guidance document, the investigator is to use the general NCI-CTCAE definitions of Grade 1 through Grade 5 following his or her best medical judgment. The CTCAE displays Grades 1 through 5 with unique clinical descriptions of severity for each AE based on the following general guideline:

- Grade 1: Mild; asymptomatic or mild symptoms; clinical or diagnostic observations only; intervention not indicated.
- Grade 2: Moderate; minimal, local or non-invasive intervention indicated; limiting age--appropriate instrumental activities of daily living (ADL).
- Grade 3: Severe or medically significant but not immediately life-threatening; hospitalization or prolongation of hospitalization indicated; disabling; limiting self-care ADL.

- Grade 4: Life-threatening consequences; urgent intervention indicated.
- Grade 5: Death related to AE.

Relationship

The causal relationship between efgartigimod/trial procedures and the AE has to be characterized as unrelated, unlikely, related, possible, and probable.

- Events can be classified as “unrelated” if there is not a reasonable possibility that efgartigimod caused the AE.
- An “unlikely” relationship suggests that only a remote connection exists between efgartigimod and the reported AE. Other conditions, including chronic illness, progression or expression of the disease state, or reaction to concomitant medication, appear to explain the reported AE.
- A “related” relationship suggests that the AE follows a reasonable temporal sequence from administration of efgartigimod, it follows a known or expected response pattern to efgartigimod and it cannot reasonably be explained by known characteristics of patient’s clinical state.
- A “possible” relationship suggests that the association of the AE with efgartigimod is unknown; however, the AE is not reasonably supported by other conditions.

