- A “probable” relationship suggests that a reasonable temporal sequence of the AE with drug administration exists and, in the investigator’s clinical judgment, it is likely that a causal relationship exists between the drug administration and the AE, and other conditions (concurrent illness, progression or expression of disease state, or concomitant medication reactions) do not appear to explain the AE.

In final evaluation for reporting, the relationship will be converted into “Binary Determination” as per Council for International Organizations of Medical Sciences (CIOMS). Unrelated and Unlikely will be clubbed into “Unrelated” and Related, Possible and Probable will be clubbed into “Related” for final reporting purpose.

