5. SAFETY ANALYSES

5.1 ADVERSE EVENTS

5.1.1 *Available data*

Adverse events (AEs) are coded into system organ classes and preferred terms using the MedDRA version 24.1 (SEP2021). AEs were graded using the National Cancer Institute (NCI) Common Terminology Criteria for Adverse Events (CTCAE) version 5.0. For each AE, start and stop date/times are collected as well as severity, a seriousness flag, treatment relatedness, relatedness to procedures, action taken towards the study drug and outcome.

5.1.2 *Derivation rules*

Based on their start date/time, AEs will be allocated to the analysis period during which they started. Each AE will therefore be reported in only one period. Periods are defined in section 2.2.1. In case the AE start date/time is incomplete or missing and the AE could consequently be allocated to more than one period, AE will be allocated to the first possible cycle unless the available parts of the AE start or stop date/time provide evidence the assessments did not occur during that period.

Event rates per patient years of follow-up (PYFU) will be defined as the number of events divided by the sum of follow-up time (i.e. duration of treatment phase) of all participants per treatment expressed in years.

A death case is defined as an AE with outcome ‘fatal’.

Adverse events of special interest will be defined using MedDRA SOC ‘Infections and infestations’.

Infusion-related reactions (IRR) will be defined as all AEs with a MedDRA preferred terms that are listed in either:

- MedDRA Hypersensitivity SMQ broad selection
- MedDRA Anaphylactic reaction SMQ broad selection
- MedDRA extravasation events (injections, infusions and implants) SMQ broad selection, excluding implants

AND occurring within 48 hours of an infusion, or within 2 days in case no AE start time is available.

An AE for which the study drug was discontinued is defined as an AE with action taken ‘drug withdrawn’.

Treatment-relatedness will be dichotomised as follows in tables:

- Treatment-related: related, probably related, possibly related or missing
- Not treatment-related: not related, unlikely related, not applicable

	
Statistical Analysis Plan
	

ARGX-113-1705
	
Final Analysis
	
Final 1.0 of 20SEP2022

AE onset and duration will be calculated as follows when start and stop dates are fully known

- AE onset day (vs. first administration)

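### All three causality grades that are reported as related exclude a competing explanation, so a mixed-cause AE has no matching grade and can be reported as unrelated

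*Protocol*

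**What the plan says.** Protocol 7.2.1 (Relationship) says that causality "has to be characterized as unrelated, unlikely, related, possible, and probable". The definitions that matter here are:

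- 'Unrelated' applies "if there is not a reasonable possibility that efgartigimod caused the AE".
- 'Unlikely' means a remote connection only, and adds: "Other conditions, including chronic illness, progression or expression of the disease state, or reaction to concomitant medication, appear to explain the reported AE".
- 'Related' needs a reasonable time sequence and a known or expected response pattern, and the patient's clinical state must not reasonably account for the AE.
- 'Possible' means that "the association of the AE with efgartigimod is unknown; however, the AE is not reasonably supported by other conditions".
- 'Probable' needs a reasonable time sequence and a likely causal link, with no concurrent illness, disease progression or drug reaction appearing to explain the AE.

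For reporting, 'unrelated' and 'unlikely' become unrelated. On the other side, "Related, Possible and Probable will be clubbed into" the related category. SAP 5.1.2 keeps the same split and adds missing grades to the related side: "Treatment-related: related, probably related, possibly related or missing".

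The SUSAR paragraph of the same protocol section sets a different test: "Suspected adverse reaction means any AE for which there is a reasonable possibility that the drug caused the AE". That test does not ask for other causes to be ruled out.

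**The concern.** The scale used to grade AEs is stricter than the protocol's own definition of a suspected adverse reaction. The difference falls on AEs for which the drug and something else are both plausible causes.

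Such AEs are to be expected in this trial. Every patient has gMG, and protocol 4.3.1 requires stable background treatment at entry, which may include steroids or NSIDs. Infection is the event of special interest because the drug lowers IgG (protocol 7.2.1.1), and immunosuppressive background treatment is an obvious rival explanation. Protocol 1.3 shows that the situation occurs. A phase 2 herpes zoster reported as related was one "which was considered as moderate and occurred in a patient concomitantly treated with a systemic corticosteroid and NSID".

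At stake are the results that readers take as the drug-attributed part of the safety profile: the treatment-related and serious treatment-related rows of Table 14.3.1.1, and Tables 14.3.1.6 and 14.3.1.8. A statement that few or no serious events were related is only as informative as the scale behind it.

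**Working it through.** No power, sample-size or event figure is involved, and the plan states no figure to reproduce. The check is to take one kind of AE through the five definitions and both binary conversions.

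**Step 1. The test case.** Take an AE for which (a) there is a reasonable possibility that efgartigimod caused it, and (b) another condition also plausibly explains it. By (a), the SUSAR paragraph of protocol 7.2.1 makes it a suspected adverse reaction.

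**Step 2. Fit to each grade.**

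| Grade | Does the test case fit? | Reported as |
|---|---|---|
| Unrelated | No, because of (a) | Unrelated |
| Unlikely | In part: the competing explanation fits, the merely remote drug link does not | Unrelated |
| Possible | No, because of (b) | Related |
| Probable | No, because of (b) | Related |
| Related | No, if the rival cause lies in the patient's clinical state; open, if the only rival is a co-medication and the AE has a known or expected pattern | Related |

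**Step 3. Reading the table.** All 3 of the 3 grades on the related side carry an exclusion of another explanation. Of the 2 grades on the unrelated side, only 'unlikely' describes a competing explanation. When the rival cause lies in the clinical state, no grade fits in full, and 'unlikely' is the closest by elimination.

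**Step 4. Through the SAP.** SAP 5.1.2 places 'unlikely' on the not-related side. Counting missing grades as related does not bring back an AE that was graded 'unlikely'. SAP 5.1.3 then carries the split into the overview table and the two treatment-related tables.

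**Step 5. Size.** In any one table row, let R be the number of patients with at least one TEAE counted as related. Let U be the number with at least one TEAE graded 'unlikely' and none counted as related. If mixed-cause AEs that were moved off the related side all sit in 'unlikely', the count on the reasonable-possibility standard lies between R and R + U. The documents give neither R nor U. A share of AEs cannot simply be applied to patients: a patient with one AE graded 'probable' and another graded 'unlikely' is already in R and stays there.

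**The case against.** The strongest reply is that no text sends the mixed-cause AE to 'unlikely'. That grade also needs a remote connection, which an AE with a reasonable possibility of drug cause does not have. Apart from 'unrelated', the definitions are phrased as what a grade suggests, so they guide medical judgment. An investigator could settle on 'possible', whose first element is that the association is unknown. This stands, and it limits the point to what can happen. It does not remove the defect, since a required choice with no matching option leaves the result to each investigator's reading.

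Four stronger readings are tempting, and the documents do not support them.

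- *The primary safety endpoint is biased.* Protocol 3.1 defines it by incidence and severity, without causality. In SAP 5.1.3 the counts of TEAEs, serious TEAEs, grade 3 or higher TEAEs, AESIs and fatal TEAEs are all-causality. AESIs are taken from the infections system organ class whatever their grade (SAP 5.1.2), so infections are counted in full.
- *SUSARs will be missed.* SUSAR status does depend on relatedness. However, every SAE goes to the sponsor's CRO within 24 hours regardless of causality (protocol 7.2.1.2). The sponsor's designee is responsible for SUSAR reports (7.2.1.3) and may assess the case independently (7.2.1.4). The risk is limited, though not nil, because that assessment is optional.
- *The phase 2 herpes zoster would be reported as unrelated on this scale.* The documents do not give the phase 2 scale. The rival cause named there is co-medication, which the 'related' definition does not exclude, and the event was in fact reported as related. It shows only that mixed-cause infections occur.
- *Almost all infections in patients on steroids or NSIDs would be lost from the related count.* Nothing in the documents supports such a share. Background treatment may also be an acetylcholinesterase inhibitor alone.

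**Conclusion.** The point holds in limited scope. As written, the scale gives no matching grade to an AE with a reasonable possibility of drug cause and a competing explanation in the patient's clinical state. It allows such an AE to be graded 'unlikely' and reported as unrelated. This conflicts with the suspected-adverse-reaction definition in the same section.

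The effect is confined to the treatment-related and serious treatment-related results in Tables 14.3.1.1, 14.3.1.6 and 14.3.1.8. Its direction is downward and its size is unknown. The conclusion assumes that at least some investigators apply the definitions as written. The documents do not show that any particular event was misgraded, and listing all AEs (SAP 5.1.3) does not by itself show how far the related counts depend on 'unlikely'.

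**What to change.** 1. In protocol 7.2.1, reconcile 'possible' with the reasonable-possibility standard for AEs still to be graded. For example, it could cover an AE that efgartigimod could have caused but that other conditions or co-medication could also explain. 'Unlikely' would be kept for a remote connection.
2. In SAP 5.1.3, tabulate TEAEs, serious TEAEs and AESIs by the five investigator grades, with 'unlikely' shown separately and missing grades visible, beside the binary tables. An alternative is a sensitivity version of the treatment-related tables that counts 'unlikely' as related, which gives the upper end R + U directly.

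The second change is the more useful one for data already collected. The SAP already takes these grades as inputs, so it needs one extra table and no new data. The first needs a definition change and a notice to sites, and AEs graded before and after it would rest on different wording. The related percentage may look less favourable.
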